### 9.3 POPULATIONS FOR ANALYSES

All analyses will be intent to treat (include all randomized participants). Sensitivity analyses will include examining sources of missing data and alternative parameter estimates under different assumptions of missing data (e.g., missing completely at random, missing at random, multiple imputation).

### 9.4 STATISTICAL ANALYSES

#### 9.4.1 GENERAL APPROACH

We are using a latent growth curve model (piecewise) to model separate change processes assumed during weight loss and post intervention. All models will be examined for goodness of fit, normality and linear (vs. Nonlinear) change. Best fit models will be interpreted for primary effects.

#### 9.4.2 ANALYSIS OF THE PRIMARY ENDPOINT(S)

Primary weight and psychosocial/health endpoints will be analyzed using the same piecewise linear growth curve model. Validity of model will be examined via BIC, AIC, and RMSEA with the later below .05 used as threshold for moving to interpretation of the model. We will test simple linear models and build complexity (non-linear, robust model estimation) based on model fit and observation of outliers and potential subgroups. Missing data will be assumed missing at random during initial model estimation and sensitivity analyses using (missing completely at random) tests to evaluate the impact of missing data.

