## 3 OBJECTIVES AND ENDPOINTS

OBJECTIVES	ENDPOINTS	JUSTIFICATION FOR ENDPOINTS
Primary		
To test the comparative efficacy of Noom Health vs. Noom Digital Health for weight loss, quality of life, psychosocial functioning, and self-reported health status.	We will conduct remote scheduled direct entry interview and self-report questionnaire data at 8 time points (Screening/Baseline, 1 month, 4 months, 6 months, 12 months, 18 months, 24 months, and 30	Hypothesis 1: Noom Health users will show 6 month efficacy relative to Noom Digital Health for weight loss at post-intervention.  Hypothesis 2: Noom Health users will show long-term (12 Month) efficacy relative to Noom Digital Health.

OBJECTIVES	ENDPOINTS	JUSTIFICATION FOR ENDPOINTS
	months). Weight data will be collected by video observed scale. Digital scales will be provided for those who do not have access.	
Secondary		
To compare potential moderators of treatment response in Noom Health vs. Digital Health subjects.	We will conduct remote scheduled direct entry interview and self-report questionnaire data at 8 time points (Screening/Baseline, 1 month, 4 months, 6 months, 12 months, 18 months, 24 months, and 30 months). Weight data will be collected by video observed scale. Digital scales will be provided for those who do not have access.	Hypothesis 1: Clinical Profile (composite moderator) will show significant interaction with treatment condition, demonstrating that individuals with a more severe profile (older, less support, more health conditions, more psychosocial problems) will benefit more from Noom Health than Digital Control.  Hypothesis 2: Weight suppression (absolute difference between highest and current weight) will moderate efficacy of Noom Health vs. Digital Education.
Tertiary/Exploratory		
To identify within treatment mechanisms of change among Noom Health group.		Hypothesis 1: Time series Bayesian belief network model of adherence will predict (a) study dropout, (b) successful weight loss, (c) quality of life.  Hypothesis 2: Regular eating will mediate treatment effects of weight loss over time.  Hypothesis 3: Self-efficacy of weight loss will mediate Noom Health vs. Noom Digital Health effects at post treatment and 12 month follow-up.

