## 9 STATISTICAL CONSIDERATIONS

### 9.1 STATISTICAL HYPOTHESES

- Primary Endpoint(s):

Hypothesis 1: Noom Health users will show 6 month efficacy relative to Noom Digital Health for weight loss at post-intervention.

Hypothesis 2: Noom Health users will show long-term (12 Month) efficacy relative to Noom Digital Health.

- Secondary Endpoint(s):

Hypothesis 1: Clinical Profile (composite moderator) will show significant interaction with treatment condition, demonstrating that individuals with a more severe profile (older, less support, more health conditions, more psychosocial problems) will benefit more from Noom Health than Noom Digital Health.

Hypothesis 2: Weight suppression (absolute difference between highest and current weight) will moderate efficacy of Noom Health vs. Noom Digital Health.

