### 10.1.9.1 DATA COLLECTION AND MANAGEMENT RESPONSIBILITIES

Source Records:

1. Measures of eating and activity:
  - a. 24 hour recall interview. Foods and beverages consumed during the 24-hour period before the assessment will be asked.
  - b. Eating Disorder Examination Questionnaire (EDE-Q). EDE-Q measures dietary restraint, eating, shape, and weight concerns, loss of control eating episodes.
  - c. International Physical Activity Questionnaire (IPAQ). The IPAQ is a brief self-report measure of time spent in an average week completing vigorous or moderate physical activity, walking, and sitting.
2. Measures of Related Symptoms:
  - a. Depression Anxiety Stress Scales (DASS). The DASS is a 42-item self-report measure of negative emotional states with subscales of depression, anxiety, and stress symptoms.
  - b. Short Form-36 Health Survey (SF-36). The SF-36 is a 31-item self-report of health-related quality of life measure that generates two scores: The Mental Composite Score (MCS), and the Physical Composite Score (PCS).
  - c. Brief Self-Efficacy Scale for Healthy Eating. The Brief Self-Efficacy Scale for Healthy Eating is a 12-item self-report of self-efficacy with scales specific to physical activity, healthful eating and weight-loss.

- d. PROMIS Sleep-Related Impairment is a self-report questionnaire that assesses sleep impairment over the last 7 days. The measure consists of 16 individual items and takes 2-5 minutes to complete.
- e. The Quality of Life, Enjoyment, and Satisfaction Questionnaire-Short Form (Q-LES-Q-SF) is a 16 self-report assessment of overall enjoyment and satisfaction with physical health, mood, work, household and leisure activities, social and family relationships, daily functioning, sexual desire/interest/performance, economic status, vision, ability to get around physically, overall well-being, medications, and contentment.

3. Noom App Data:

- a. Adherence: Both local and global adherence will be measured. Local adherence will be the percent of completed versus expected activities in each of the available categories (i.e., ((# completed/# expected) x 100%)), including: self-monitoring, activity levels, reading psychoeducational materials, problem solving, etc.). Global adherence will be measured with a similar calculation for virtual attendance/contact with scheduled coach check-ins.

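### Several outcomes are primary with no ranking or error-control rule, and the model that yields the primary effect is chosen from the outcome data, with no rule if none passes the fit threshold

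*Combined protocol and SAP*

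**What the plan says.** Section 3 gives one primary objective covering four domains: "To test the comparative efficacy of Noom Health vs. Noom Digital Health for weight loss, quality of life, psychosocial functioning, and self-reported health status". Section 9.4.2 carries this into the analysis: "Primary weight and psychosocial/health endpoints will be analyzed using the same piecewise linear growth curve model".

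Section 9.1 lists two primary hypotheses. The first concerns weight at 6 months: "Noom Health users will show 6 month efficacy relative to Noom Digital Health for weight loss at post-intervention". The second concerns 12 months and names no outcome: "Noom Health users will show long-term (12 Month) efficacy relative to Noom Digital Health".

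Sections 9.1 to 9.4.9 state no significance level, sidedness, order of testing, success rule or multiplicity adjustment. No score is named for the three non-weight domains. Section 10.1.9.1 offers several candidates: the Q-LES-Q-SF, three DASS subscales, and the SF-36, which "generates two scores: The Mental Composite Score (MCS), and the Physical Composite Score (PCS").

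On the model, Section 9.4.1 says "Best fit models will be interpreted for primary effects". Section 9.4.2 starts from simple linear models and will "build complexity (non-linear, robust model estimation) based on model fit and observation of outliers and potential subgroups". It makes fit a condition of interpretation: "RMSEA with the later below .05 used as threshold for moving to interpretation of the model". No default model is named, and no reporting rule covers the case in which every model stays at or above .05.

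**The concern.** There are two separate gaps.

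The first is error control. With several outcomes called primary, two primary times and no statement of what counts as success, a positive trial could be declared on whichever primary result is significant. No false-positive rate can be attached to that claim. Section 9.2 powers the psychosocial outcomes separately from BMI, so they cannot be set aside as incidental.

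The second is the estimate itself. The piecewise family is prespecified, but the form interpreted within it is settled after looking at the outcome data, partly on outliers and possible subgroups. The arm difference that answers each hypothesis is therefore not fixed beforehand. If no form passes the threshold, the plan as written gives no primary result to report. Section 6.3 says participants are not blinded, and most non-weight outcomes are self-reported, so the rule should be settled before arms are compared.

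**Working it through.** **1. How many primary tests?** The documents allow at least three readings:
- 2 tests: weight at 6 and 12 months.
- 5 tests: weight at 6 months, as Hypothesis 1 says, and all four domains at 12 months, because Hypothesis 2 names none.
- 8 tests: four domains at both times.

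**2. Family-wise error.** The plan gives no error rate to reproduce. Assumptions, none of them in the plan: two-sided 5% per test, any one success counts, all nulls true. For k independent tests the chance of at least one significant result is 1 − 0.95^k, and of at least one favouring Noom Health 1 − 0.975^k. For equal correlation .8, I simulated 1,000,000 draws of correlated normals with cut-off 1.96.

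| Tests | Either direction, r = .8 | Either direction, r = 0 | Favouring Noom Health, r = .8 | Favouring Noom Health, r = 0 |
|---|---|---|---|---|
| 2 | .078 | 1 − .95² = .098 | .039 | .049 |
| 5 | .128 | 1 − .95⁵ = .226 | .064 | .119 |
| 8 | .158 | 1 − .95⁸ = .337 | .079 | .183 |

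**3. The RMSEA threshold.** A model passes if its chi-square is below df + df(N − 1)(.05)². With N = 600, complete data and an assumed 32 df (8 visits, three growth factors, a treatment predictor, free residual variances), the cut-off is 32 + 32 × 599 × .0025 = 79.92. Under true RMSEA e the statistic is noncentral chi-square with noncentrality df(N − 1)e². The pass probability is above .999 for a correct model, .892 at e = .04, .523 at .05 and .122 at .06. With 39 df (equal residual variances) the last three are .912, .521 and .097. So the threshold bites only if real misfit remains in the final model.

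**4. Would misfit remain?** Section 4.3 expects most participants to reach maximal loss within 3-4 months, so a straight first piece to month 6 may misfit. Illustration, with assumed inputs: mean BMI loss 1.65 (5% of a BMI of 33), 90-100% of it reached by month 4, SD 4.5, compound-symmetry correlation .8-.95.
- Straight first piece: misfit of the mean alone gives RMSEA .03-.09, with pass probability from .996 to below .001.
- Quadratic first piece, one form that the plan's non-linear step could take: RMSEA .003-.008 and pass probability above .9999.

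**5. Does the form move the estimate?** Take an assumed arm difference of 0, 0.2 and 0.8 at months 0, 1 and 4, then 0.8 to month 30. I fitted it by generalised least squares with the baseline difference fixed at 0, under several covariance structures. The month-6 estimate is 0.80-0.89 with a straight first piece and 0.80-0.84 with a quadratic first piece.

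**6. Stated power for the proposed contrast.** With a knot at month 6, the month-6 arm difference in change is 6 × (difference in first slope), so testing one is testing the other. Section 9.2 states power .942 for within-treatment BMI change (0.8, SD 4.5). That simulation cannot be rerun, because its alpha, variance components and correlations are not given. A two-sample t-test at two-sided 5% has noncentrality (0.8/4.5)√(n/2) and gives .585 at 300 per arm and .443 at 210 per arm (30% missing). A growth model may be more precise, so this gap does not prove an error. No power is stated for month 12; the follow-up figure of 85% is for 24 months.

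**The case against.** **The test count is open.** A reader might infer that all four domains are primary at both times, making 34% the trial's error rate. The documents do not say that. Hypothesis 1 confines month 6 to weight, and Hypothesis 2 names no outcome. Both hypotheses are directional, so two-sided figures also count errors against Noom Health, and requiring both hypotheses to succeed would hold the error at or below 5%. All of this stands. What also stands is that the plan does not choose between these readings.

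**The plan does escalate when fit is poor.** A reader might infer from the early plateau in Section 4.3 that the threshold will probably block the primary result. Step 4 does not support that, since a non-linear first piece would probably repair this misfit. The gap is narrower: no default model, and no rule if escalation fails.

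**Selecting on fit is not selecting on the treatment p-value.** A reader might infer inflated type I error or a badly biased estimate. The first cannot be computed from the documents. On the second, step 5 shows little movement between two piecewise forms. A single quadratic across all visits would give 0.40-0.55 at month 6 in the same example, but it is not piecewise, and fit would tend to disfavour it.

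**The knot.** Section 4.1 refers to 12 months of intervention, and the Section 1.3 schedule row runs to Day 365. Month 6 is nevertheless the dominant reading, since Section 9.1 ties post-intervention to 6 months. This needs clarifying and is not a defect of the same weight.

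**Conclusion.** The concern holds in this form. Weight, quality of life, psychosocial functioning and self-reported health are all primary and unranked, at two times, with no alpha, order, success rule or multiplicity rule. Under the stated assumptions family-wise error runs from 8-10% (2 tests) through 13-23% (5 tests) to 16-34% (8 tests), or 4-5%, 6-12% and 8-18% counting only errors that favour Noom Health. Which range applies cannot be settled from the documents.

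Independently, the model interpreted for primary effects is chosen from outcome data behind a fit threshold with no reporting rule if it is never met. The documents do not show that failure is likely or that the choice inflates type I error by any known amount. They do show that the primary contrast is not fixed in advance and could go unreported. Both gaps bear on what counts as trial success, so they should be closed before arms are compared.

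**What to change.** Before arms are compared:
- Name one lead primary outcome: the between-arm difference in weight change, expressed as BMI change because Section 9.2 powers BMI.
- State two-sided 5% and one error-control rule. One option is month 6, then month 12, in fixed sequence, followed by one named score per remaining domain with Holm. Scores named in Section 10.1.9.1 would serve: the Q-LES-Q-SF, one stated DASS subscale and one SF-36 composite. Other valid procedures would do.
- Make the piecewise linear model with its knot at month 6 the default, and reconcile Sections 1.3, 4.1 and 9.1 on when intervention ends for this purpose.
- Report its model-implied arm differences at months 6 and 12 as the primary results whatever the fit. Give RMSEA, BIC and AIC as diagnostics, and treat non-linear, robust and subgroup-driven models as supportive.

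The cost is analysis-plan wording, with no added visits. Later outcomes face a stricter threshold, and in the sequence above every later test depends on month 6. The stated .942 should therefore be checked against the 59% and 44% from the simple test, and power at month 12 should be added. If power is judged too low, another order may suit better. The amendment should be dated and should say whether outcome data by arm had been seen, since Section 5.2 shows that recruitment had already closed when the protocol was last changed there.

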#### 9.4.3 ANALYSIS OF THE SECONDARY ENDPOINT(S)

The same modeling approach will be used for secondary endpoints and moderator models will include first, estimation of latent factor based on demographic variability and the interaction of this latent variable and treatment estimated as formal hypothesis test.

#### 9.4.4 SAFETY ANALYSES

N/A

#### 9.4.5 BASELINE DESCRIPTIVE STATISTICS

Baseline variables (demographics and anthropometrics) will be compared at baseline using t-tests and chi-square to determine if pre-treatment bias exists in randomization.

#### 9.4.6 PLANNED INTERIM ANALYSES

N/A—no interim analysis planned.

#### 9.4.7 SUB-GROUP ANALYSES

Our moderator analyses rely on empirically derived profiles (as opposed to p-hacking search for group difference) to maximize likelihood of identifying meaningful differences between relevant individuals.

#### 9.4.8 TABULATION OF INDIVIDUAL PARTICIPANT DATA

Data will be tabulated in person-period format.

#### 9.4.9 EXPLORATORY ANALYSES

We will utilize repeated measures Bayesian belief network to establish adherence within the Noom group and examine its changes to relationship over time. BBNs are most often used to establish greatest

predictive value related to available data and tested against randomly sampled (80-20) develop and test data sets.

Our Mediation model of weekly regular eating is a time series mediation model and assumes latent measure of meal-snack adherence will mediate changes in weight and included a time-varying set of latent variables that change in parallel to our primary outcome.

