## 4 STUDY DESIGN

### 4.1 OVERALL DESIGN

The study will: (a) test the Noom app in coach led groups with individuals interested in weight loss to determine if it significantly improves weight loss, quality of life, psychosocial functioning, and self-reported health status compared to a control.

We will use a randomized-controlled design comparing the Noom app administered in groups (6 months) to Digital Control with 6 months active maintenance in both groups. The proposal allows for a critical test of effect of Noom on relevant outcomes in the population.

All participants will complete a brief survey indicating that they would like to be contacted and includes a study description and availability. Then they will complete informed consent via a HIPAA-compliant videoconference (Zoom) and questionnaires on REDCap. Eligible participants will be randomized to one of two groups for 6 months intervention and 6 months maintenance (12 months of intervention): (1) Noom app with coaching (Noom Health; n=300), or (2) Digital Control (Noom Digital Health; n=300). We anticipate screening 684 subject to reach our recruitment goal of 600.

Participants' procedures:

- screening survey to determine eligibility and Baseline/Pre-intervention Zoom call
- Assessments: 24 hour recall interview, EDE-Q, Q-LES-Q-SF, IPAQ, Brief Self-Efficacy Scale for Healthy Eating, DASS, SF-36, PROMIS, Demographics and Smartphone Comfort

Intervention:

Noom Health participants will use Noom for 6 months of intervention and 6 months of maintenance (12 months total). Participants will use the app multiple times per day to log eating episodes (the number of episodes will vary by person). The features include diet, physical activity, and weight tracking, a social media group in the app, access to coaches, and personalized coach feedback. Coaches will interact with participants directly through the app. Participants will be encouraged to use the app for 6 months after intervention to maintain weight loss, with goal to maintain weight.

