### 9.2 SAMPLE SIZE DETERMINATION

Mt. Sinai will use piecewise latent growth curve models with treatment as primary indicator. Using Monte Carlo simulation studies with 10,000 draws and 6 time points and 2 growth processes, Mt. Sinai evaluated sample size needed to detect significant differences on each growth process (within treatment, post-treatment follow-up). Mt. Sinai also varied missing at random patterns of missing of data at 10%, 20% and 30% increasing linearly over each timepoint. The results indicate that with 30% missing data, mean difference in BMI change of 1.2 (SD =4.5), Mt. Sinai is 85% powered to detect significant difference at 24 month follow-up with N = 600. The power increases substantially for within treatment BMI change .8 (SD =4.5), power = .942. For psychosocial outcomes, N=600 with same parameters indicated 82-90% power to find treatment effects at 24 months, assuming a .20 SD unit difference between groups. Within treatment, the same difference is powered 90-98%.

For Aim 2, Mt. Sinai assumed full information on all moderators and tested the interaction effect with a composite moderator profile of 12 indicators. The interaction between latent moderator (M) and treatment was powered at .93 and .85 with N=600, and 30% attrition for within treatment and follow-up.

For Aim 3 power analyses were based on a 13-item adherence measure adapted from the Noom Monitor (Binge Eating) study and assumes network efficiency of .75. Mt. Sinai would examine the relationship between network entropy and the outcomes, with statistical power for the regression prediction at 100% for each outcome. Mediation model of weekly regular eating is a time series mediation model and assumes latent measure of meal-snack adherence will mediate changes in weight. The calculation is based on effect size goal of .25, .5, and .75. The results of simulations suggest that power for the smallest effect size (.25) is approximately .80 with 10% missing data or less and moderate correlations between time and change in regular eating (.3) and moderate correlation between regular eating and weight outcome (.3).

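### The only validation named for the adherence network is a random 80-20 split in a 300-person arm; by participant this tests on about 60, and the unit of splitting is unstated

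*Combined protocol and SAP*

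**What the plan says.** The exploratory objective in section 3 is "To identify within treatment mechanisms of change among Noom Health group". Its first hypothesis is "Time series Bayesian belief network model of adherence will predict (a) study dropout, (b) successful weight loss, (c) quality of life". Section 9.4.9 keeps the model to one arm: "We will utilize repeated measures Bayesian belief network to establish adherence within the Noom group". Sections 4.1 and 6.1.1 put 300 people in that arm.

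On validation, 9.4.9 says only that such networks are "tested against randomly sampled (80-20) develop and test data sets". It gives no number of splits, no cross-validation, no unit of splitting and no performance measure. Section 9.4.8 adds that the data are held in person-period form, so each participant supplies several rows.

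On power, section 9.2 "assumes network efficiency of .75" for this aim, says the study team "would examine the relationship between network entropy and the outcomes", and gives "statistical power for the regression prediction at 100% for each outcome". It states no effect size, alpha or N for that regression.

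**The concern.** A 20% hold-out from 300 people is small. Accuracy measured on it would have a wide interval, and would vary with which people happened to be drawn. The plan asks for this accuracy for three outcomes, so imprecision affects all of the network's predictive results.

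The unstated unit adds a risk in the other direction. If rows rather than people are split, the test rows belong to people the model has already seen, and the reported accuracy will look better than it would in new users.

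The power statement matters for a different reason. An unqualified 100% reads as assurance about the whole aim, yet a reader cannot tell what association it assumes or how many people it rests on.

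**Working it through.** **Inputs from the protocol.** Noom Health arm 300 (4.1, 6.1.1); split 80-20 (9.4.9); eight assessment times (1.1, 1.3); person-period data (9.4.8).

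**Assumptions, because the plan gives no figure.** AUC 0.75 as the performance measure for a binary outcome; 30% events; two-sided 5% for power. The 30% attrition is stated in 9.2 for other aims and is used here only as a range.

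**1. Size of the test set, split by participant.** 0.20 × 300 = 60 for testing and 240 for development. If 30% lack the outcome, 300 × 0.70 = 210, and 0.20 × 210 = 42. The 210 and 42 do not apply to dropout, because people who drop out have that outcome observed.

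**2. Precision of the AUC (Hanley-McNeil).** With A = 0.75, Q1 = A/(2 − A) = 0.600 and Q2 = 2A²/(1 + A) = 0.6429. A² = 0.5625, so Q1 − A² = 0.0375 and Q2 − A² = 0.0804. For n₁ events and n₀ non-events,

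SE² = [A(1 − A) + (n₁ − 1)(Q1 − A²) + (n₀ − 1)(Q2 − A²)] / (n₁n₀).

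- 60 people (18 and 42): (0.1875 + 0.6375 + 3.2946)/756 = 0.00545, so SE = 0.074. The 95% half-width is 1.96 × 0.074 = 0.14, an interval of about 0.61 to 0.89.
- 300 people (90 and 210): (0.1875 + 3.3375 + 16.7946)/18,900 = 0.001075, so SE = 0.033. The half-width is 0.06, an interval of about 0.69 to 0.81.

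Range on 60 people: with 20% events (12 and 48), SE = √(4.377/576) = 0.087; with 50% (30 and 30), SE = √(3.605/900) = 0.063. The comparison depends little on the event rate, since the ratio of standard errors is close to √(300/60) = 2.2 throughout.

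The 0.033 treats 300 cross-validated predictions as if they came from one fixed model. Fold models share training data, so it is approximate.

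**3. Split by row.** Suppose the rows are the eight assessments and each row goes to the test set with probability 0.20. The chance that a person has at least one test row is 1 − 0.8⁸ = 0.83. The chance that all eight rows are test rows is 0.2⁸, about 0.000003. Practically everyone in the test set would also be in the development set.

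**4. The 100% power.** It cannot be reproduced, because its inputs are missing. What can be found is the correlation it would need. Taking 100% as at least 99.5% after rounding, and using the Fisher z approximation for one predictor and a continuous outcome,

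r = tanh[(1.960 + 2.576)/√(n − 3)].

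- n = 300: tanh(4.536/17.23) = tanh(0.263) = 0.26.
- n = 210: tanh(4.536/14.39) = tanh(0.315) = 0.31.

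Power by effect size is Φ[atanh(r)√(n − 3) − 1.960]:

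| r | n = 300 | n = 210 |
|---|---|---|
| 0.1 | 41% | 30% |
| 0.2 | 94% | 83% |
| 0.3 | 99.96% | 99% |

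So the stated figure is attainable in the whole arm for a moderate correlation, but not for a small one.

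**The case against.** **The plan does not say there is one split.** This is correct. The sentence in 9.4.9 reads as a description of how such networks are usually tested, and it is silent on repetition. A reader might infer that the result hangs on one draw of 60 people. That is the ordinary reading of an 80-20 develop/test scheme, but it is not plan text, and 60 also assumes splitting by participant. What remains is that no other scheme is offered.

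**The 60 people do not refute the 100%.** A reader might set the two side by side and conclude that the power claim is false: on 60 people, power at r = 0.25 is only 49%, and 99.5% needs r of 0.54. The documents do not support that conclusion. Section 9.2 attaches the figure to the regression of outcomes on network entropy, and nothing confines that regression to the test set. The r = 0.25 is a reviewer's choice; the .25 in 9.2 belongs to the separate regular-eating mediation model. The network efficiency of .75 is undefined, but if it were a correlation, power would be about 100% even on 42 people. The figure is therefore unsupported, not shown to be wrong.

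**Correlation power does not suit every outcome.** This also stands. Dropout is binary, successful weight loss appears to be, and dropout is not lost to attrition. The thresholds above apply to a continuous outcome such as a quality-of-life score.

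**The aim is exploratory, and the validation method is partly preference.** No treatment comparison rests on this accuracy, so the stakes are low. But cross-validation by participant gives a more precise estimate from the same data, and the unit of splitting is a matter of validity.

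**Conclusion.** The point holds as a weakness in validation and a gap in specification, of minor importance. On the ordinary reading, the network is tested on about 60 people, and an AUC near 0.75 would carry a standard error of about 0.074, a little over twice the roughly 0.033 available if all 300 contribute. This rests on a participant-level hold-out, an assumed AUC of 0.75 and an assumed 30% event rate. If rows are split instead, the accuracy would be inflated, by an amount the documents do not allow one to compute.

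The 100% power is a separate matter. It lacks an effect size, alpha and N, and needs a correlation of at least about 0.26 (300 people) or 0.31 (210 people) for a continuous outcome. The primary and secondary analyses are not affected.

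**What to change.** In 9.4.9, replace the 80-20 split with repeated 10-fold cross-validation over all Noom Health participants. Form the folds by participant, so that all rows of one person stay together. Carry out every model-building step, including structure learning and variable selection, inside the folds. State the number of repeats and the performance measure for each of the three outcomes. Each fold then develops on 270 people and tests on 30, and everyone is used for testing once per repeat.

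In 9.2, replace the 100% with power by effect size, and state the alpha, the N and what the network efficiency of .75 means. The table above could serve for a continuous outcome. Give dropout its own calculation, with all 300 participants, a stated dropout rate and a measure suited to a binary outcome. Successful weight loss needs the same treatment if it is defined as a yes/no outcome.

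The cost is more computing time and revised text in two sections. No new data are needed.
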